3.6.3.5 Overall Improvement / Overall Improvement and Stability

Overall improvement rate will be analyzed, which is defined as the proportion of participants who have achieved an overall improvement as defined in Section 3.4.3 PRO Endpoints. Stratified Miettinen and Nurminen's method will be used for comparison of the overall improvement rate between the treatment groups. The difference in overall improvement rate and its 95% CI from the stratified Miettinen and Nurminen's method with strata weighting by sample size will be provided. The stratification factors used for randomization (See Section 6.3.2 of protocol) will be applied to the analysis.

The point estimate of overall improvement rate will be provided by treatment group, together with 95% CI using exact binomial method by Clopper and Pearson (1934) [\[6\]](#).

The same method will be used to analyze overall improvement and stability rate, which is defined as the proportion of participants who have achieved overall improvement and stability as defined in Section 3.4.3 PRO Endpoints.

3.6.3.6 Analysis Strategy for Key PRO Endpoints

A summary of the primary analysis strategy for key PRO endpoints is provided in [Table 7](#).

Table 7 Analysis Strategy for Key PRO Variables

Endpoint/Variable	Statistical Method	Analysis Population	Missing Data Approach
Mean change from baseline in EORTC QLQ-C30 
 • Global health status/QoL • Physical functioning • Appetite loss EORTC QLQ-CR29 
 • Bloating And EQ-5D VAS	cLDA model	FAS	Model-based.
TTD in EORTC QLQ-C30 
 • Global health status/QoL • Physical functioning • Appetite loss And EORTC QLQ-CR29 
 • Bloating 	Stratified log-rank test and HR estimation using stratified Cox model with Efron's tie handling method	FAS	Censored according to rules in Table 6 .
CCI			
Abbreviations: cLDA = constrained longitudinal data analysis, FAS = full analysis set, TTD = time to deterioration, HR = hazard ratio, QoL = quality of life.			

3.6.4 Demographic and Baseline Characteristics

The comparability of the treatment groups for each relevant demographic and baseline characteristic will be assessed by the use of tables and/or graphs. No statistical hypothesis tests will be performed on these characteristics. The number and percentage of participants screened and randomized and the primary reasons for screening failure and discontinuation will be displayed. Demographic variables, baseline characteristics, primary and secondary diagnoses, and prior and concomitant therapies will be summarized by treatment either by descriptive statistics or categorical tables.

3.7 Interim Analyses

The eDMC will serve as the primary reviewer of the results of the IAs and will make recommendations for discontinuation of the study or modification to the executive oversight committee of the Sponsor. If the eDMC recommends modifications to the design of the protocol or discontinuation of the study, this executive oversight committee and potentially

other limited Sponsor personnel may be unblinded to the treatment level results in order to act on these recommendations. The extent to which individuals are unblinded with respect to results of IAs will be documented by the unblinded statistician. Additional logistic details will be provided in the eDMC Charter.

Treatment-level results of the interim analysis will be provided by the unblinded statistician to the eDMC. Prior to final study unblinding, the unblinded statistician will not be involved in any discussions regarding modifications to the protocol or statistical methods, identification of protocol deviations, or data validation efforts after the IAs.

Efficacy Interim Analysis

One IA is planned in addition to the FA for this study. For the IA and FAs, all randomized participants will be included. Results of the IAs will be reviewed by the eDMC. Details of the boundaries for establishing statistical significance with regard to efficacy are discussed further in Section 3.8.

The analyses planned, endpoints evaluated, and drivers of timing are summarized in [Table 8](#).

Table 8 Summary of Interim and Final Analyses Strategy

Analyses	Key Endpoints	Timing	Estimated Time after First Participant Randomized	Primary Purpose of Analysis
IA	OS (PFS and ORR if OS is rejected)	Both ~260 OS events have been observed and ~ 7 months after last participant randomized	~ 18 months	
• Interim OS analysis• Final PFS and ORR analysis
FA	OS	both ~336 OS events have been observed and ~ 7 months after interim analysis	~ 25 months	
• Final OS analysis

Abbreviations: FA = final analysis; IA = interim analysis; ORR = objective response rate; OS = overall survival; PFS = progression free survival.

3.7.1 Safety Interim Analysis

[figure not shown]
The eDMC will be responsible for periodic interim safety reviews as specified in the eDMC charter. An interim safety analysis will be performed 6 months since first participant is randomized. Afterwards, the eDMC will review safety data periodically in the study. Interim safety analyses will also be performed at the time of interim efficacy analyses. Details will be specified in the eDMC charter.

3.8 Multiplicity

The study uses the graphical method of Maurer and Bretz [2] to provide strong multiplicity control for multiple hypotheses as well as interim analyses. According to this approach, study hypotheses may be tested more than once, and when a particular null hypothesis is rejected, the α allocated to that hypothesis can be reallocated to other hypothesis tests. Note that if the OS null hypothesis is rejected at FA of the study, the previously computed PFS and ORR test statistics at IA may be used for inferential testing with its updated bounds considering the α reallocation from the OS hypothesis. Figure 1 shows the initial 1-sided α allocation for each hypothesis in the ellipse representing the hypothesis. The weights for reallocation from each hypothesis to the others are shown in the boxes on the lines connecting hypotheses.

Figure 1 Multiplicity Diagram for Type I Error Control

Abbreviations: ORR = objective response rate; OS = overall survival; PFS = progression-free survival.

Note: If OS null hypothesis is rejected, the allocation strategy allows testing of PFS and ORR at $\alpha = 0.0125$, separately.

3.8.1 Overall Survival

The study will test OS at IA and FA. Following the multiplicity strategy

CCI

A large black rectangular redaction box covers the bottom portion of the text, with the text 'CCI' in red at the top left corner.

Table 9 Efficacy Boundaries and Properties for Overall Survival Analyses

Analysis	Value	$\alpha=0.025$
IA: 77%* N: 434 Events: 260 Month: 18	Z	2.2976
	p (1-sided) ^a	0.0108
	HR at bound ^b	0.7517
	P(Cross) if HR=1 ^c	0.0108
	P(Cross) if HR=0.7 ^d	0.7185
FA N: 434 Events: 336 Month: 25	Z	2.0177
	p (1-sided) ^a	0.0218
	HR at bound ^b	0.8022
	P(Cross) if HR=1 ^c	0.0250
	P(Cross) if HR=0.7 ^d	0.9000

Abbreviations: HR = hazard ratio; IA = interim analysis, FA = final analysis.
The number of events and timings are estimated.
*Percentage of total planned events at the interim analysis.
^a p (1-sided) is the nominal α for group sequential testing.
^bHR at bound is the approximate HR required to reach an efficacy bound.
^cP(Cross if HR=1) is the probability of crossing a bound under the null hypothesis.
^dP(Cross if HR=0.7) is the probability of crossing a bound under the alternative hypothesis.

The bounds provided in the table above are based on the assumptions that the expected number of events at IA and FA are 260 and 336, respectively. At the time of an analysis, the observed number of events may differ substantially from the expected. To avoid overspending at an IA and leave reasonable α for the FA, the minimum α spending strategy will be adopted. At an IA, the information fraction used in Lan-DeMets spending function to determine the alpha spending at the IA will be based on the minimum of the expected information fraction and the actual information fraction at each analysis. Specifically,

- In the scenario that the events accrue slower than expected and the observed number of events is less than the expected number of events at a given analysis, the information fraction will be calculated as the observed number of events at the IA over the target number of events at FA.
- In the scenario that the events accrue faster than expected and the observed number of events exceeds the expected number of events at a given analysis, then the information fraction will be calculated as the expected number of events at the IA over the target number of events at FA.

The final analysis will use the remaining Type I error that has not been spent at the earlier analyses. The observed event counts for all analyses will be used to compute correlations.

Of note, while the information fraction used for alpha spending calculation will be the minimum of the actual information fraction and the expected information fraction, the correlations required for deriving the bounds will still be computed using the actual information fraction based on the observed number of events at each analysis over the target number of events at FA.

The minimum spending approach assumes timing is not based on any observed Z-value and thus the Z test statistics used for testing conditioned on timing are multivariate normal. Given the probabilities derived with the proposed spending method, the correlations based on actual event counts are used to compute bounds that control the Type I error at the specified alpha level for a given hypothesis conditioned on the interim analysis timing. Since this is true regardless of what is conditioned on, the overall Type I error for a given hypothesis unconditionally is controlled at the specified level. By using more conservative spending early in the study, power can be retained to detect situations where the treatment effect may be delayed.

3.8.2 Progression-free Survival

The study will test PFS at IA only if the OS null hypothesis is rejected. Following the multiplicity strategy as outlined in [Figure 1](#), the PFS hypothesis may be tested at $\alpha=0.0125$ (if the OS null hypothesis is rejected, but not the ORR hypothesis) or at $\alpha= 0.025$ (if both the OS and ORR null hypothesis is rejected). [Table 10](#) shows the boundary properties for each of these α levels for the PFS analysis. Note that the final row indicates the total power to reject the null hypothesis for PFS at each α level.

Table 10 Efficacy Boundaries and Properties for Progression-Free Survival Analyses

Analysis	Value	$\alpha=0.0125$	$\alpha=0.025$
IA N = 434 Events*: 404 Month: 18	Z	2.2414	1.9600
	p (1-sided) ^a	0.0125	0.025
	HR at bound ^b	0.8000	0.8227
	P(Cross) if HR=1 ^c	0.0125	0.025
	P(Cross) if HR=0.65 ^d	0.9820	0.9912

Abbreviations: HR = hazard ratio; IA = interim analysis.

*The number of events and timing is estimated.

^ap (1-sided) is the nominal α for group sequential testing.

^bHR at bound is the approximate HR required to reach an efficacy bound.

^cP (Cross if HR=1) is the probability of crossing a bound under the null hypothesis.

^dP(Cross if HR=0.65) is the probability of crossing a bound under the alternative hypothesis.

3.8.3 Objective Response Rate

The study will test ORR only once at the IA if the OS null hypothesis is rejected. Following the multiplicity strategy as outlined in [Figure 1](#), the ORR hypothesis may be tested at $\alpha=0.0125$ (if the OS null hypothesis is rejected, but not the PFS hypothesis) or at $\alpha= 0.025$ (if both the OS and PFS null hypothesis is rejected). Power at the possible α -levels as well as the approximate treatment difference required to reach the bound (Δ ORR) are shown in [Table 11](#), assuming underlying [CCI](#) response rates in the control and experimental groups, [CCI](#).

Table 11 Possible α Levels and Approximate ORR Difference Required to Demonstrate Efficacy for Objective Response at IA

α	$\sim\Delta$ Objective Response Rate (ORR)	Power (Δ ORR=0.1)
0.0125	0.0549	0.970
0.025	0.0480	0.985

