3.9 Sample Size and Power Calculations

The study will randomize 434 participants in a 1:1 ratio into the lenvatinib plus pembrolizumab arm the SOC arms. OS are primary endpoint for the study, with PFS and ORR as the key secondary endpoints.

For the OS endpoint, based on a target number of 336 events and 1 IA at approximately 77% of the target number of events, [CCI](#) at the initially allocated $\alpha=0.025$ (1-sided).

For the PFS endpoint, based on a target number of 404 events at the IA (final PFS analysis), the study has [CCI](#) at the reallocated $\alpha=0.0125$ (1-sided) if OS hypothesis is rejected.

Based on the 434 participants with at least 7 months of follow-up, the power of the ORR testing at the reallocated $\alpha=0.0125$ (1-sided) if OS hypothesis rejected is approximately 97.0% to detect a 10-percentage point difference between [CCI](#).

Note that the above power calculations are based on a constant HR assumption.

Based on CORRECT and RE COURSE studies, the above sample size and power calculations for OS and PFS assume the following:

CCI

- Enrollment period of 11 months with enrollment ramp-up over first 2 months.
- CCI
- A follow-up period of 14 and 7 months and for OS and PFS, respectively, after the last participant is randomized.

CCI

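### Does Table 11 overstate the ORR difference needed for significance by fixing the variance at the design alternative?

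*SAP*

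**What the plan says.** Section 3.8.3 tests ORR once, at the interim analysis, after OS is rejected. The level is 0.0125, rising to 0.025 "if both the OS and PFS null hypothesis is rejected". Table 11, whose title ends "Approximate ORR Difference Required to Demonstrate Efficacy for Objective Response at IA", gives, for each level, an approximate difference at the bound and the power for a true difference of 0.10. The rows read "0.0125 0.0549 0.970" and "0.025 0.0480 0.985". The text conditions them on assumed "response rates in the control and experimental groups"; the values are redacted. Section 3.9 repeats the power at 0.0125 as "approximately 97.0% to detect a 10-percentage point difference" and gives the sample size: "The study will randomize 434 participants in a 1:1 ratio". Section 3.6.1.3 and Table 3 name the stratified M&N method as the ORR test.

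**The concern.** The M&N test of no difference uses a variance evaluated at the observed response rates under the null. Table 11 instead appears to use the variance that applies when the true difference is the full 10 points. A result at the bound shows only about half that difference. If the control arm performs as planned, the pooled rate at the bound is then lower, the standard error is smaller, and a smaller difference is enough to reject. ORR is an alpha-controlled hypothesis, so a reader comparing an observed difference of, say, 4.6 points with the printed 5.49 could conclude that it misses 0.0125 when the planned test would reject.

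**Working it through.** **Inputs.** 434 participants randomised 1:1, taken as n = 217 per arm (section 3.9). One-sided alpha 0.0125 and 0.025, so z = 2.2414 and 1.9600. Printed bounds 0.0549 and 0.0480, and powers 0.970 and 0.985 (Table 11). The response rates are redacted and are back-solved below as an assumption. Stratification is not modelled.

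**Reproducing the table.**
- Implied standard error: 0.0549/2.2414 = 0.0245 and 0.0480/1.9600 = 0.0245. One fixed variance serves both rows.
- Pooled form: SE² = 2p(1−p)/217, so p(1−p) = 0.0245² × 217/2 ≈ 0.0651 and p = 0.070. With a 10-point difference this means 2% against 12%.
- Bounds at those rates: 2.2414 × 0.02449 = 0.0549 and 1.9600 × 0.02449 = 0.0480.
- Power: Φ((0.10 − bound)/SE₁), with SE₁ = √((0.02×0.98 + 0.12×0.88)/217) = 0.0240, gives 0.970 and 0.985.

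All four figures reproduce. Neighbouring control rates do not fit at alpha 0.0125: 1.5% gives 0.0530 with power 0.979, and 2.5% gives 0.0567 with power 0.960.

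**Letting the variance follow the observed rates.** Hold the observed control rate at c and solve d / √(2p(1−p)/217) = z with p = c + d/2.

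| Observed control rate | Required d, alpha 0.0125 (printed 0.0549) | Required d, alpha 0.025 (printed 0.0480) |
|---|---|---|
| 1% | 0.0353 | 0.0291 |
| 2% | 0.0429 | 0.0360 |
| 3% | 0.0488 | 0.0413 |
| 4% | 0.0538 | 0.0457 |
| 5% | 0.0581 | 0.0495 |

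At a control rate of 2% the printed values are 0.0120 too high in both rows. An observed difference equal to the printed bound would have one-sided p = 0.0036 or 0.0074. The printed and required values agree at a control rate of about 4.3% (alpha 0.0125) or 4.6% (alpha 0.025). Above that the printed values are too low.

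**Other ways of fixing the rates.**
- With the observed pooled rate at 7%, the printed bounds give p = 0.0125 and 0.0250.
- With the experimental arm observed at 12%, the required differences are 0.0614 and 0.0546, and the printed bounds give p = 0.024 and 0.045.

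**Integer counts** (score test with the M&N factor 434/433).
- 4/217 against 14/217, 4.6 points: p = 0.008, which rejects at 0.0125.
- 6/217 against 16/217, the same 4.6 points: p = 0.0144, which does not.

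**Power of the score test at 2% and 12%,** by exact binomial enumeration: 98.5% and 99.3%, against the printed 97.0% and 98.5%.

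**The case for a change.** The best case for a change is that the back-solve is tight and the discrepancy at the planning control rate is not small. The printed 0.0549 is 28% above 0.0429 (0.0549/0.0429 = 1.28), and 0.0480 is 33% above 0.0360 (0.0480/0.0360 = 1.33), yet the column is printed to four decimals. For the printed bounds to be right, the control arm would have to respond at about twice its planning rate. A table headed as the difference required should arguably be right when the control arm behaves as assumed, and correcting it would take two numbers and a footnote.

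The arithmetic in that argument stands. What does not stand is calling the table an error. For a binomial endpoint no single difference is the bound, because the critical difference moves with the observed rates. Evaluating the variance at both design rates is one ordinary planning convention, and holding only the control rate at its design value is another. The SAP says its figures are approximate and rest on assumed rates in both groups, which is the first convention. Substituting 0.043 would give a value that is too low as soon as the control arm responds above 2%: at 3% the required difference is already 0.049.

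**Conclusion.** The mechanism is as suspected: Table 11 uses the pooled variance at the design alternative. If the observed control rate is 2%, the printed differences exceed what an unstratified score test needs by about 1.2 points. That size rests on a control rate inferred from redacted text and on the control arm being observed exactly there. Over 1% to 5% the discrepancy at alpha 0.0125 runs from 2.0 points too high to 0.3 too low, and at alpha 0.025 from 1.9 too high to 0.15 too low.

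Nothing in the trial turns on the column. The stratified M&N p-value is compared with the alpha that the graph in section 3.8 assigns, so the test and its type I error are untouched. The stated power errs on the safe side. Anyone reporting ORR will have the p-value itself and no reason to read significance off a planning table. A footnote naming the variance convention would be harmless, but it would change no result or conclusion, so the plan can stand as written.

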3.8.4 Safety Analysis

The eDMC has responsibility for assessment of overall risk/benefit. When prompted by safety concerns, the eDMC can request corresponding efficacy data. eDMC review of efficacy data to assess the overall risk/benefit to study participants will not require a multiplicity adjustment typically associated with a planned efficacy IA.

3.9 Sample Size and Power Calculations

The study will randomize 434 participants in a 1:1 ratio into the lenvatinib plus pembrolizumab arm the SOC arms. OS are primary endpoint for the study, with PFS and ORR as the key secondary endpoints.

For the OS endpoint, based on a target number of 336 events and 1 IA at approximately 77% of the target number of events, [CCI](#) at the initially allocated $\alpha=0.025$ (1-sided).

For the PFS endpoint, based on a target number of 404 events at the IA (final PFS analysis), the study has [CCI](#) at the reallocated $\alpha=0.0125$ (1-sided) if OS hypothesis is rejected.

Based on the 434 participants with at least 7 months of follow-up, the power of the ORR testing at the reallocated $\alpha=0.0125$ (1-sided) if OS hypothesis rejected is approximately 97.0% to detect a 10-percentage point difference between [CCI](#).

Note that the above power calculations are based on a constant HR assumption.

Based on CORRECT and RE COURSE studies, the above sample size and power calculations for OS and PFS assume the following:

CCI

- Enrollment period of 11 months with enrollment ramp-up over first 2 months.
- CCI
- A follow-up period of 14 and 7 months and for OS and PFS, respectively, after the last participant is randomized.

CCI

3.10 Subgroup Analyses

To determine whether the treatment effect is consistent across various subgroups, the between-group treatment effect for OS, PFS, and ORR (with a nominal 95% CI) will be estimated and plotted by treatment group within each category of the following subgroup variables:

- Geographic region (Asia vs. Western Europe/North America vs. Rest of World)
- ECOG performance status (0, 1)
- Age category (<65 years, \geq 65 years)
- Sex (female, male)
- Race (white, all others)
- Presence of liver metastasis (Yes, No)
- PD-L1 expression level (CPS \geq 1, CPS<1)
- BRAF (wild type, mutant)
- RAS (wild type, mutant)
- Investigators' choice of standard of care chemotherapy prior to randomization (Regorafenib versus TAS102)

The consistency of the treatment effect will be assessed using descriptive statistics for each category of the subgroup variables listed above. If the number of participants in a category of a subgroup variable is less than 10% of the ITT population, the subgroup analysis will not be performed for this category of the subgroup variable, and this subgroup variable will not be displayed in the forest plot. The subgroup analyses for OS and PFS will be conducted using an unstratified Cox model, and the subgroup analyses for ORR will be conducted using the unstratified Miettinen and Nurminen method.

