3.5.1 Efficacy Analysis Populations

The ITT population will serve as the primary population for the analysis of efficacy data in this study. The ITT population consists of all randomized participants. Participants will be analyzed in the treatment arm to which they are randomized. Details of the approach to handling missing data are provided in Section 3.6.1.4.

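### Does the 10% rule wrongly remove geographic region from the forest plot when only one region is small?

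*SAP*

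**What the plan says.** SAP Section 3.10 plans treatment effects for OS, PFS and ORR, with nominal 95% confidence intervals, that "will be estimated and plotted by treatment group within each category of the following subgroup variables". Ten variables are listed. Nine have two categories. The exception is "Geographic region (Asia vs. Western Europe/North America vs. Rest of World").

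The small-category rule is one sentence with a condition and two consequences:

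- Condition: "If the number of participants in a category of a subgroup variable is less than 10% of the ITT population".
- Analysis: "the subgroup analysis will not be performed for this category of the subgroup variable".
- Display: "this subgroup variable will not be displayed in the forest plot".

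The section also says that consistency of effect is assessed descriptively for each category, with unstratified Cox models for OS and PFS and the unstratified Miettinen and Nurminen method for ORR.

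The size of the analysis set comes from Section 3.9 ("The study will randomize 434 participants in a 1:1 ratio") and Section 3.5.1 ("The ITT population consists of all randomized participants").

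**The concern.** The two consequences work at different levels. A small category loses its own analysis, but the whole variable loses its place on the plot. For a two-category variable this is harmless: if one level is below 10%, the other is more than 90% of the ITT population and its estimate nearly repeats the overall result.

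With three regions that argument can fail. Two large regions could each give a usable estimate, yet both would leave the figure because a third region recruited poorly. The section exists to show whether the effect is consistent, and regional consistency is a question readers ask of a multinational trial. The imprecision that justifies a 10% threshold belongs to the small region, not to the other two.

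**Working it through.** **Inputs.** ITT size 434 (Sections 3.9 and 3.5.1). Target deaths at the final analysis 336 (Section 3.9: "based on a target number of 336 events and 1 IA at approximately 77% of the target number of events"). Threshold 10% (Section 3.10). Regional shares are not given, so every split below is an assumption.

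**Check of the approximation.** The rule has no figure of its own to reproduce. The intervals below take the variance of a log hazard ratio as 4/D for D deaths under 1:1 allocation, which can be tested on the hazard ratios at the bounds in Table 9:

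- Final analysis: exp(−2 × 2.0177/√336) = 0.802; the plan states 0.8022.
- Interim: exp(−2 × 2.2976/√260) = 0.752; the plan states 0.7517.

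The approximation agrees with the plan to three decimals.

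**When the rule is triggered.** 0.10 × 434 = 43.4, so a category of 43 or fewer falls under it (43/434 = 9.9%). The remainder is 434 − 43 = 391, or 90.1%. With deaths in proportion to participants, 391 × 336/434 ≈ 303.

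**What the omitted rows would show.** For a region of n participants, D = n × 336/434. With an observed hazard ratio of 0.70, the 95% interval is 0.70 × exp(±1.96 × 2/√D).

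| Assumed region size | Deaths | 95% CI |
|---|---|---|
| 195 (even split of the remainder) | 151 | 0.51 to 0.96 |
| 130 (uneven split, smaller region) | 101 | 0.47 to 1.03 |
| 261 (uneven split, larger region) | 202 | 0.53 to 0.92 |
| 48 (second region just above threshold) | 37 | 0.37 to 1.33 |
| 43 (the region that triggers the rule) | 33 | 0.35 to 1.38 |

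**When the loss is material.** There are three cases once the rule is triggered.

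1. One region below 10% and two sizeable ones (rows 1 to 3). Two reasonably informative rows leave the plot.
2. One region below 10% and a second just above it, for example 43 and 48. The third has 434 − 43 − 48 = 343, or 79% of ITT, and largely repeats the overall result. The second is almost as imprecise as the one excluded. Little is lost.
3. Two regions below 10%. The third has at least 434 − 2 × 43 = 348, or 80.2%. As with a two-category variable, little is lost.

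Only the first case costs anything. The pooled 391 participants and 303 deaths are not the information in any single regional row, so they overstate what disappears.

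**What the rule does not remove.** The sentence stops the analysis for the small category only. The other two regions are still estimated, and the section's assessment of consistency rests on descriptive statistics by category, not on the figure alone.

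**The case for a change.** The strongest case for a change is that the display rule works against the section's own purpose for the one variable with three categories, that Section 3.10 names no table where the remaining regional estimates would appear, and that one sentence would put it right. Settling a display rule before results are known is also better than adjusting it afterwards. Calling the rule a common convention does not fully answer this, since the rationale fits two-category variables.

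Much of that stands. The literal reading is the natural one, the mismatch of levels is real, and an exception for region would be cheap. The second phrase may be loose shorthand for the category just mentioned, in which case this is a slip of wording, but the text does not settle it.

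What does not stand is that the regional comparison would be hidden or suppressed. It would be absent from one figure while still being produced. Nor is there any sign that the trigger is likely. The figure of about 100 for the China subpopulation does not help, because it includes extension participants whom Section 3.5 excludes from the global populations.

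**Conclusion.** The observation is right as a reading of Section 3.10, but it calls for no change. At most, if exactly one region had 43 or fewer of 434 participants and the other two were both sizeable, two rows would be missing from a descriptive forest plot although their estimates had been produced. That rests on a hypothetical regional split, on deaths proportional to participants, and on 1:1 allocation within region.

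The OS, PFS and ORR tests, their alpha allocation, the power and the ITT analysis are untouched. Subgroup intervals are nominal and support no formal claim. An analyst who meets this situation can report the two remaining regions from the analyses the sentence already leaves in place. Keeping them on the plot is a reasonable preference about display, and it would alter no estimate or conclusion.
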